##### **7.4.1. When the test started**

Signed informed consent.

Inclusion criteria and exclusion criteria.

Medical history was collected and the status of medication was inquired.

Routine physical examination.

Routine laboratory tests: Routine blood examination (including erythrocyte count, leukocyte count, hemoglobin, platelet count, proportion of monocytes, lymphocytes and neutrophils), urine routine (erythrocyte, leukocyte, urine protein), liver and kidney function (including ALT, AST, TBIL, BUN, CR), pregnancy test (women of child-bearing age), and other laboratory examination.

Combination medication was recorded.

Assigned random numbers.

### **8. Observation of side effect**

#### **8.1. Definition**

Side effect: Any adverse medical event that occurred between the time patients signed the informed consent and were enrolled in the trial and the last follow-up, regardless of whether there was a causal relationship with the experimental vaccine, was considered as side effect.

Serious side effect: Any side effect and hematological and/or other laboratory abnormalities that occur that lead to the use of targeted medical care.

#### **8.2. Criteria for determining the severity of side effect**

When completing the side effect table for CRF, the investigator would use mild, moderate, and severe to describe the intensity of the side effect. For unified standards, side effect intensity was classified as follows:

Mild: Did not affect daily life;

Moderate: Affected daily life;

Severe: Severe affected on daily life.

Be careful to distinguish between the severity and intensity of side effect. Severe was used to describe intensity and was not necessarily a serious side effect (SAE). For example, a headache might be severe in intensity but might not be classified as a serious side effect (SAE) unless it met SAE criteria.

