## 7.3. Security indicators

General data: physical examination

Laboratory examination: Routine blood examination (including erythrocyte count, leukocyte count, hemoglobin, platelet count, proportion of monocytes, lymphocytes and neutrophils), urine routine (erythrocyte, leukocyte, urine protein), liver and kidney function (including ALT, AST, TBIL, BUN, Cr).

Symptoms accompanying any discomfort were recorded by the investigator

a) No: No symptoms

- b) Mild: Weak symptoms sometimes appeared
- c) Moderate: persistent but not noticeable after distraction
- d) Severe: Persisting no matter when

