#### 10.2.6. Contents of statistical analysis

The statistical analysis plan was written by the statistician, finalized before the database lock, and consisted of a variety of tables. The main contents of the analysis included:

Case distribution: different data sets in each group, case distribution in each center, comparison of total abscission rate, and detailed list of termination causes.

Comparability analysis: compared demographic data with other base-value indicators to measure the comparability of the two groups.

Effectiveness analysis:  $X^2$  test and t test were used for main indicators and global indicators. Since this study was a multi-center clinical trial, central effect on the efficacy indicators should be considered in the analysis.

Analysis of the factors affecting the efficacy: such as age, sex, disease type, disease condition and so on, there were significant differences between the two groups before the use of vaccine, or if there were significant related factors that affected the vaccine effect, these factors should be used as co-factors when comparing the vaccine effect between the two groups for variables,

---

covariance analysis or Logistic regression analysis was required. The combination of medication and so on needed a detailed list.

Safety analysis: firstly, according to the requirements of side effect correlation, the side effect and adverse reactions of the two groups were listed and described (including the number of cases of various side effects, the number of cases and the conversion rate of "normal to abnormal" or "abnormal intensification" of laboratory test indicators before and after the test), and the reasons and explanations were listed.

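### Section 8.2 grades side-effect intensity only by effect on daily life, and 10.2.6 counts laboratory shifts without size, so the plan does not summarise how many subjects had large asymptomatic laboratory abnormalities

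*Combined protocol and SAP*

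**What the plan says.** Section 8.2 sets a single intensity scale for the side-effect table of the case report form: "For unified standards, side effect intensity was classified as follows". The three grades are "Mild: Did not affect daily life", "Moderate: Affected daily life" and "Severe: Severe affected on daily life". The section separates intensity from seriousness, and its example is a headache. It has no criterion for laboratory results.

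Section 8.1 counts any adverse medical event between consent and last follow-up as a side effect. It defines a serious side effect as "Any side effect and hematological and/or other laboratory abnormalities that occur that lead to the use of targeted medical care".

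Section 7.3 lists the blood, urine, liver and kidney tests. It also gives a second scale, for symptoms that accompany discomfort, running from "a) No: No symptoms" to "Severe: Persisting no matter when". Section 7.4 schedules the laboratory tests at D0, D7, D14, D21 and D28.

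For the analysis, 10.2.6 lists "the number of cases and the conversion rate of 'normal to abnormal' or 'abnormal intensification' of laboratory test indicators before and after the test", together with reasons and explanations. Section 11.1 has each centre submit its normal ranges and its own criteria for abnormality, and has a physician verify markedly deviant values.

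**The concern.** Safety is a stated objective, and the laboratory panels are the main safety data that do not depend on what a subject reports. The subjects are healthy, so a change in liver enzymes, creatinine or a blood count may well go unnoticed by the person concerned. A scale that asks only about daily life carries no information about such an event.

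If intensity grades are used when side effects are described, a statement that no laboratory side effect was moderate or severe could follow from the scale and not from the data. The laboratory analysis in 10.2.6 does not make up for this, because it counts shifts and does not size them.

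**Working it through.** The plan states no figure on this point, so the check sets the provisions side by side and asks what each does with an abnormal result that causes no symptoms.

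| Section | Criterion | Result for an asymptomatic abnormality | Shows size? |
|---|---|---|---|
| 8.2 intensity | Effect on daily life | Mild, if recorded as a side effect | No |
| 7.3 symptom scale | Presence and persistence of symptoms | No symptoms; the scale does not address laboratory values | No |
| 8.1 and 8.4 seriousness | Targeted care, outcome or medical judgement | Serious or not serious | No |
| 10.2.6 laboratory analysis | Becomes abnormal, or worsens | One case | No |
| 11.1 physician check | Marked deviation | Verified and explained, not graded | Not as a summary |
| 10.2.2 descriptive statistics | Mean, SD, maximum, minimum, median and so on | An extreme may appear, if applied to laboratory data | Partly |

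**Illustration (assumed values, not trial data).** Take five subjects who are normal at D0, have no symptoms and have their result recorded as a side effect: ALT at 1.1, 3 and 10 times the upper limit, and platelets at 0.9 and 0.3 times the lower limit. Under 8.2 all five are Mild. Under 10.2.6 each is one conversion from normal to abnormal. If ALT is already 1.1 times the limit at D0, a rise to 3 times and a rise to 10 times each count as one worsening. The grades follow from assuming no symptoms, so this shows how the rules work and says nothing about how often the situation arises.

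**Do the generic descriptive statistics close the gap?** Compare two sets of three subjects, all normal at D0, with worst ALT values of 1.1, 1.1 and 10 times the limit in one set, and 10, 10 and 10 in the other.

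- Conversions: 3 in each set.
- Maximum: 10 in each set.
- Subjects at 10 times the limit: 1 in the first set, 3 in the second.

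The means differ: (1.1 + 1.1 + 10) / 3 = 4.07 against 10. But a mean and standard deviation over all subjects cannot be read back as a number of subjects with a large abnormality. Raw maxima are also not tied to each centre's own limit.

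**The case against.** The strongest case on the other side has four parts.

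**Recording.** The plan does not say that every abnormal laboratory result is entered as a side effect and given an intensity. Sections 4.1, 8.1 and 10.2.6 name laboratory abnormalities alongside side effects, so 8.2 may be meant for clinical events only. This stands as a limit on the claim. A reader might infer that every asymptomatic abnormality is graded Mild. The documents support that only for results recorded as side effects, and they do not say when that happens.

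**Reporting.** A reader might also infer that a severity table will conceal large abnormalities. No such table is planned. Section 8.2 refers to a table on the case report form, and 10.2.3 promises only a descriptive analysis of side effects. This objection stands too.

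**Other routes.** Abnormalities that lead to targeted care are serious under 8.1 whatever their intensity. Section 8.4 adds medical judgement, 11.1 has marked values verified, 4.1 has significant abnormalities at the end of the study followed to normal, and 10.2.2 and 10.2.4 provide for extremes and for tables and graphs of repeated measurements. By these routes a marked value could well come to light. None of them classifies abnormalities by size or counts subjects by size.

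**The later analysis plan.** Section 10.2.6 leaves the tables to an analysis plan finalised before database lock, where a table by grade could be added. It could, but nothing in the text requires it, and cut points chosen then would be chosen after results had begun to arrive.

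**Conclusion.** The point holds in a limited form. The only intensity scale for side effects gives no information on a laboratory event without symptoms, and the planned laboratory analysis counts occurrence and worsening without size. The plan therefore does not summarise how many subjects had large abnormalities. It does not follow that such abnormalities would go unreported.

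The conclusion on grading assumes that the result is entered as a side effect. The conclusion on 10.2.6 does not need that assumption.

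No numerical size can be given. The plan states no expected rate of laboratory abnormality, and the number of laboratory values collected counts measurements, not misgraded events. The values themselves are kept, so the summary could be rebuilt later, but it would then not be prespecified. Reconciling the 8.2 and 7.3 scales would not cure the gap, because neither measures a laboratory result.

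**What to change.** - **Section 8.2:** limit the daily-life scale to symptomatic events. Grade numeric laboratory results by the worst post-dose value relative to the centre's normal limit, and also relative to D0 where D0 is already abnormal. Use one published laboratory toxicity scale, named before the first dose and applied at all centres. For semi-quantitative urine results, use that scale's own categories.
- **Section 10.2.6:** for each analyte, tabulate D0 grade against worst post-dose grade.

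The tests are already scheduled in 7.3 and 7.4, and 11.1 already collects the centre normal ranges, so no new test or visit is needed. The cost is a change of wording and one extra table. The downside is that some events now called mild may be reported at a higher grade. The change concerns grading and reporting only and leaves clinical management as it is.

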### 8.3. Criteria for determining the relationship between side effect and the study vaccine

The causal analysis of the relationship between all side effect (including serious side effect and general side effect) and the test vaccine was judged according to the five grades of almost certain, probable, possible, unlikely and unrelated. The first three side effects were defined as side effect to the vaccine. The following five aspects were causal analysis took into consideration:

Was there a reasonable sequential relationship between the time of initiation and the occurrence of a suspected vaccine side effect (ADR) (appear when using vaccine).

Did the suspected ADR conform to the type of ADR known to vaccines (consistent with the literature).

Whether the suspected ADR could be explained by the effect of combination medication, previous medication, the subject's clinical status, or other therapies (other explanations).

Did the suspected ADR disappear or decrease after a period of discontinuation of the vaccine.

Whether suspicious ADR reappear (reuse) after re-exposure to the same vaccine.

Causes analysis were carried out according to the following table, and the factors considered in the table were shown in the corresponding numerical table above.

Factors	1 Appear when use vaccine	2 Same as reference	3 Other causes	4 Disappear when stop vaccine	5 Reappear when reuse
Almost certain	+	+	-	+	+
Probable	+	+	-	+	?
Possible	+	+	±	±	?
Unlikely	+	-	±	±	?
Unrelated	-	-	+	-	-

The investigator should evaluate the possible association between side effect and the test vaccine and its combination using the following 5-level classification criteria:

**Almost certain:** Evidence of use of experimental vaccine; The chronological sequence of the occurrence of side effect and the administration of the experimental vaccine was reliable; The occurrence of side effect was more reasonably explained by the experimental vaccine than by other causes; The repeated vaccine test was positive; The pattern of side effect was consistent with what had been known about this or such vaccine.

**Probable :** Evidence of use of the experimental vaccine; The chronological sequence of the occurrence of side effect and the administration of the experimental vaccine was reliable; side effect were more likely to be explained by the experimental vaccine than by other causes.

**Possible :** Evidence of use of experimental vaccine; The chronological sequence of the occurrence of side effect and the administration of the experimental vaccine was reliable; Side effect might be caused by the experimental vaccine or by other causes.

---

Unlikely: Evidence of use of the experimental vaccine; Side effect were more likely to be caused by other causes; Repeated vaccine tests were negative or equivocal.

Unrelated: Patients did not take the experimental vaccine; Or the time sequence of the occurrence of side effect and the administration of the experimental vaccine could not be trusted; Or there were other significant causes that could lead to side effect.

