## 4. Overall design and arrangement of the test

### 4.1. Test design

This study adopted a one-arm experimental design. The whole study mainly collected qualified normal healthy people without disease from the hospital, and excluded people with basic diseases such as hypertension, diabetes, hyperlipidemia and so on. Once confirmed, they were assigned to administer 1 dose of Bacillus subtilis spore. Follow-up observation and efficacy examination were performed on days 7, 14, 21 and 28.

If subjects had significant laboratory abnormalities or side effect at the end of the study, they should be followed up to normal.

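### Section 8.3 grades causality by a table and by written definitions that disagree on reaction types not known for vaccines, and does not say which prevails

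*Combined protocol and SAP*

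**What the plan says.** Section 8.3 grades every side effect on five levels and then fixes which levels count: "The first three side effects were defined as side effect to the vaccine". These are *Almost certain*, *Probable* and *Possible*.

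It gives two instructions for reaching a grade. The first points to a table of five factors: "Causes analysis were carried out according to the following table". Factor 2 in that table is agreement with what is already described: "Did the suspected ADR conform to the type of ADR known to vaccines (consistent with the literature".

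The second instruction comes directly after the table: "The investigator should evaluate the possible association between side effect and the test vaccine and its combination using the following 5-level classification criteria". Written definitions of the same five grades follow. Only the definition of *Almost certain* asks for a known pattern: "The pattern of side effect was consistent with what had been known about this or such vaccine". *Probable* asks for exposure, reliable timing and the vaccine as the likelier explanation. *Possible* asks for exposure, reliable timing and no more than this: "Side effect might be caused by the experimental vaccine or by other causes". *Unlikely* asks that other causes be more likely, together with a negative or equivocal repeat test.

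Elsewhere, Section 8.1 records every adverse event as a side effect whatever its cause. Section 10.2.3 plans a descriptive analysis of side effects. Section 10.2.6 starts the safety analysis from the causality assessment and lists both side effects and adverse reactions.

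**The concern.** Safety is one of the two stated objectives, and the Introduction describes an engineered spore that carries a viral protein domain on its surface. A reaction of an unfamiliar type is one of the things such a study should be able to detect and attribute. If precedent in the literature is a condition for attribution, an unfamiliar reaction cannot be attributed, however clear its timing and however completely other causes are ruled out.

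The written definitions do not impose that condition. Two investigators could each follow Section 8.3, assess the same event and disagree on whether it is an adverse reaction to the vaccine. Section 10.2.6 describes the study as multi-centre, so the choice could also differ between centres. At stake are the meaning of the reported adverse-reaction count and, if the table is used, a downward bias in it for new reaction types.

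**Working it through.** The plan states no figure on this point, so there is none to reproduce. The check has two parts: a count over the table, then the table set beside the definitions.

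**Inputs: the table in Section 8.3**

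| Grade | 1 Timing | 2 Known type | 3 Other cause | 4 Resolves on stopping | 5 Recurs on reuse | Counted? |
|---|---|---|---|---|---|---|
| Almost certain | + | + | - | + | + | yes |
| Probable | + | + | - | + | ? | yes |
| Possible | + | + | ± | ± | ? | yes |
| Unlikely | + | - | ± | ± | ? | no |
| Unrelated | - | - | + | - | - | no |

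The *Possible* and *Unlikely* rows are identical except in factor 2.

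**Step 1: count the patterns.** Let factors 1, 3 and 4 each be + or -, and let factor 5 be +, - or unknown. For a fixed value of factor 2 this gives 2 × 2 × 2 × 3 = 24 patterns. With timing plausible (factor 1 = +) there are 2 × 2 × 3 = 12. Read ± as either value. The table does not say whether ? means any value or literally unknown, so both readings are run. Where several rows fit, the highest grade is taken.

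| Factor 1 = + | ? means any value | ? means unknown |
|---|---|---|
| Factor 2 = +: counted grade | 12 of 12 (1 + 2 + 9) | 5 of 12 (1 + 1 + 3) |
| Factor 2 = +: no row fits | 0 of 12 | 7 of 12 |
| Factor 2 = -: counted grade | 0 of 12 | 0 of 12 |
| Factor 2 = -: *Unlikely* | 12 of 12 | 4 of 12 |
| Factor 2 = -: no row fits | 0 of 12 | 8 of 12 |

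The sums in brackets are *Almost certain* + *Probable* + *Possible*. When factor 1 is -, no counted row fits at all. So with factor 2 = -, 0 of 24 patterns reach a counted grade under either reading. In the table, factor 2 is a gate.

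**Step 2: one event, two grades.** Take a reaction of a type not known for vaccines, with plausible timing, no other cause, resolution and no re-exposure. Its pattern is + - - + ?.

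| | Table | Written definitions |
|---|---|---|
| No other cause | *Unlikely*, not counted | *Probable*, counted |
| Another cause also plausible | *Unlikely*, not counted | *Possible*, counted |

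The written *Unlikely* does not fit this event unless other causes are the likelier explanation. The table allows *Unlikely* with no other cause at all, because factor 3 is ± in that row.

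**Step 3: effect on the reported rate.** Let n be the number of subjects in the safety population and r the number with at least one reaction counted under both sets of criteria. Let k be the number of further subjects whose only qualifying reaction is of a new type. The table gives r/n and the definitions give (r + k)/n, a difference of k/n. The documents give neither n nor k. The difference is zero if no such reaction occurs.

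**The case against.** The strongest reply is that the written definitions are there, that the investigator is told to use them, and that they handle a new reaction sensibly. On that view the table is only a summary. This shows that the outcome is not fixed. It does not show that the definitions prevail, because the instruction to use the table is just as direct and nothing ranks the two.

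A reader might draw stronger conclusions that the documents do not support:

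- **That the related-event rate is biased downward as the plan stands.** This follows only if the table is applied.
- **That new reactions disappear from the safety data.** Sections 8.1, 10.2.3 and 10.2.6 record, describe and list all side effects, and serious-event reporting in Section 8.5 does not depend on the causality grade. Only the label of vaccine reaction is at risk.
- **That almost any reaction to this product is new, because the protocol lists no profile for it.** Factor 2 refers to vaccines in general, and the *Almost certain* text also admits similar vaccines. Types familiar from other vaccines can score a plus. The symptoms in Section 7.2.2 are items to observe and are not named as the reference for factor 2.
- **That a single dose makes factors 4 and 5 unassessable and so removes events from the count.** Section 4.1 says "they were assigned to administer 1 dose of Bacillus subtilis spore" and Section 4.2 also has a single administration, but Summary item 3 and Section 6.3 have it once a day. Whichever holds, *Possible* accepts ± on factor 4 and ? on factor 5, so these two factors do not affect whether an event can reach a counted grade.
- **That no control group exists to show an excess.** Summary item 4 and Section 4.1 describe one arm, while Sections 6.3, 10.2.3 and 10.2.6 describe a control group or two groups.

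**Conclusion.** The point holds as an internal contradiction. For a reaction of a type not known for vaccines, with plausible timing and no likelier other cause, the table gives a grade outside the counted set and the definitions give one inside it. Section 8.3 does not say which to use. The adverse-reaction count is therefore undetermined for such events, and it is biased downward for them if the table governs.

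The table excludes all of these events from the count, but the number of subjects concerned is unknown. The conclusion assumes that ± means either value. It does not depend on how ? is read, on the number of doses or on whether there is a control group. The effect is limited to attribution and does not touch the capture of events.

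**What to change.** State in Section 8.3 that the written definitions govern and that the table is an aid to them. Amend the table so that a minus on factor 2 does not by itself exclude *Possible* or *Probable*, for example by entering ± there, and keep the plus only as support for *Almost certain*. With that change the *Unlikely* row would overlap *Possible*, so rest it on factor 3, as its written definition does. Where both the vaccine and another cause are plausible, the text decides. Define what ? means in the factor 5 column. Carry the same wording into the case report form instruction.

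The cost is a short wording change and one form instruction. Some more events will be labelled related, so the adverse-reaction count may rise.

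Separately, reconcile the dosing passages (Summary item 3 and Section 6.3 against Sections 4.1 and 4.2) and the one-arm passages with those describing a control group. How factors 4 and 5 can be assessed depends on the dosing passages. The change to factor 2 does not need to wait for either.

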### 2. Test objective

The efficacy and safety of B. subtilis spore were evaluated with simulated oral tablet as control

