### **6.3. Administration**

Test group: Oral approach, 1 capsule B. subtilis spore once a day. No other medication.

Start in the morning on an empty stomach.

Control group: Oral approach, 1 simulated tablet once a day. No other medication.

Start in the morning on an empty stomach.

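### If there is a simulated-tablet control group, section 8.3 read literally lets none of its events count as adverse reactions, which would distort the attributed part of the two-group safety summary

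*Combined protocol and SAP*

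**What the plan says.** Section 8.3 has five causality grades. For the lowest, the text reads "Unrelated: Patients did not take the experimental vaccine", followed by two alternatives joined by *or*. The definition of Possible, the lowest grade that counts, opens with "Evidence of use of experimental vaccine; The chronological sequence of the occurrence of side effect and the administration of the experimental vaccine was reliable". Probable, Almost certain and Unlikely also begin by requiring evidence that the experimental vaccine was used. On which grades count, the section says "The first three side effects were defined as side effect to the vaccine"; these are Almost certain, Probable and Possible.

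For the safety analysis, section 10.2.6 states that "the side effect and adverse reactions of the two groups were listed and described", and ties this to the causality grading.

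The documents disagree on whether there is a second group:

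- **Two groups.** Summary section 2 says "The efficacy and safety of B. subtilis spore were evaluated with simulated oral tablet as control", and main-body section 3 repeats this. Section 6.3 has "Control group: Oral approach, 1 simulated tablet once a day". Section 10.2.3 plans a superiority comparison of experimental and control groups, and section 10.2.6 refers to two groups throughout.
- **One arm.** Summary section 4 and section 4.1 describe a single-arm design, and the treatment table in section 4.2 lists only a test group.

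Section 10.2.1 refers to double-blind treatment when it defines the ITT population. It defines the safety population by use of the study vaccine.

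**The concern.** A control group shows how often headaches, fevers or stomach complaints occur without the vaccine. That works only if an event is attributed by the same rule in both groups. The rule in section 8.3 asks first whether the subject took the experimental vaccine, and in a two-group trial that is the same as asking which group the subject is in. Background events would then be able to count as reactions in the test group but not in the control group. A reader of the attributed table would take the test group's background rate as harm caused by the vaccine.

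**Working it through.** The plan states no sample size, allocation ratio or expected reaction rate, so it has no figure to reproduce. The check traces the rule and then gives the size of its effect in general terms.

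**Step 1: can a control event reach a counted grade under the literal text?**

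| Grade (8.3) | Needs evidence of use of the experimental vaccine? | Counts as a reaction? | Open to a simulated-tablet subject? |
|---|---|---|---|
| Almost certain | Yes | Yes | No |
| Probable | Yes | Yes | No |
| Possible | Yes | Yes | No |
| Unlikely | Yes | No | No |
| Unrelated | No; not having taken it is enough alone | No | Yes, the only one |

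The decisive word is the connective: "Unrelated: Patients did not take the experimental vaccine; Or the time sequence of the occurrence of side effect". Because the conditions are alternatives, the first settles the grade whatever the timing or other causes. The factor table in 8.3 agrees: the four upper grades all carry a plus for onset with vaccine use, and Unrelated carries a minus.

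**Step 2: what does this do to the attributed table?**

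Let q_T and q_C be the proportions of test and control subjects with an event that a grader applying one rule to both groups would call at least Possible.

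- Arm-neutral grading: difference = q_T − q_C.
- Literal 8.3: difference = q_T − 0 = q_T.
- Overstatement: q_T − (q_T − q_C) = q_C, the control group's background rate.

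With no true harm, q_T = q_C = q. The correct difference is q − q = 0, and the table shows q − 0 = q. Values of q are assumptions:

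| Assumed q | Test, literal rule | Control, literal rule | Apparent difference | Arm-neutral difference |
|---|---|---|---|---|
| 2.5% | 2.5% | 0% | 2.5 points | 0 |
| 5% | 5% | 0% | 5 points | 0 |
| 10% | 10% | 0% | 10 points | 0 |
| 20% | 20% | 0% | 20 points | 0 |

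**Step 3: which outputs are affected?**

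- Section 8.1 counts side effects whatever their cause, and section 10.2.6 lists side effects as well as adverse reactions. The all-cause listing by group does not pass through the clause and is unchanged.
- Section 10.2.3 plans only a description of side effects. With no safety test planned, a false-positive probability would describe an analysis that is not in the plan, so none is given.

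**Step 4: does the safety population change the picture?**

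Section 10.2.1 admits subjects who used the study vaccine. If that term excludes the simulated tablet, control subjects drop out of the safety population and the table has no control column, rather than a column of zeros. If it includes the tablet, the column exists and step 2 applies whenever *experimental vaccine* in 8.3 is still read strictly. Neither outcome gives a usable attributed comparison.

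**The case against.** A reader might infer that the control group's reaction rate is zero by definition and that the safety comparison is therefore biased. The documents do not support that, for four reasons.

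1. **There may be no control group.** Summary section 4 and sections 4.1 and 4.2 describe one arm. In a one-arm trial the clause reaches only subjects who have not yet been dosed, for example events between consent and intake, and does no harm. This stands. It makes the point conditional but does not remove it, because settling the design in favour of a control would leave the clause in place.
2. **A blinded grader cannot apply the clause by arm.** Under the double-blind treatment named in section 10.2.1, the investigator would not know who took the vaccine, and nothing in the plan provides for regrading after unblinding. This also stands. The zero arises only if grades are set or reset with knowledge of allocation; otherwise the clause cannot be operated as written. The contents list a blinding section, but the body has none that says when or by whom grading is done blind.
3. **The vaccine terms are loose.** Section 6.4 says *study vaccine* where the parallel list in section 11.1 says *experimental vaccine*, and both lists put the control tablet under *clinical trial vaccine*. Section 8.3 itself moves between *study*, *test* and *experimental* vaccine. The strict reading may therefore not be intended. That is a fair reading, but it leaves investigators free to grade control events in different ways, which is itself a reason to define the term.
4. **All-cause events by group are already planned.** This is correct, so the controlled safety question can still be answered from them. Only the attributed part of the summary is exposed.

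**Conclusion.** The point holds in conditional form. If the trial has the control group that the objective and sections 6.3, 10.2.3 and 10.2.6 describe, and if section 8.3 is applied literally with knowledge of allocation, no control event can count as an adverse reaction. The attributed table would then overstate the vaccine's excess by the control background rate graded at least Possible. With no true harm, the whole displayed difference would be spurious: 2.5 to 20 percentage points for assumed background rates of 2.5% to 20%. The documents give no rates, so the actual size is unknown.

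The documents do not show that the safety analysis as a whole is biased, or that the control column will in fact be zero. The all-cause listing is sound on this point, and no safety test is planned that the artefact could push to significance. This is a defect of definition, worth correcting because the correction is nearly free.

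**What to change.** First reconcile the one-arm and two-group descriptions. The wording then follows from that decision.

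**If a control group is kept:**

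- In 8.3, define relatedness in all five grades by reference to the assigned study product, meaning spore capsule or simulated tablet.
- In 8.3, limit the not-taken condition under Unrelated to events that began before any study product was taken.
- In 8.3, state that grading is done without knowledge of group, and that grades are not reset after unblinding.
- In 10.2.6, base the between-group safety comparison on all side effects regardless of causality, with the graded table as supportive.
- In 10.2.1, make clear that *study vaccine* in the safety population includes the simulated tablet.

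**If the trial is single-arm:** delete the two-group adverse-reaction summary from 10.2.6 and report all side effects with exact confidence intervals.

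The cost is wording in three sections, with no extra subjects, visits or data. The small downside is that some control events will be listed as related, which is what a blinded causality assessment should be expected to produce.
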